- s. Site staff is to administer the C-SSRS, SBQ-R and PHQ-8 to all subjects at screening and score immediately. Subjects who have recent or active suicidal ideation or behavior or clinically significant depression will be excluded from the study or discontinued from the study per [Section 4.2](#), [Section 7.5.1](#), [Section 7.5.2](#) and [Section 7.5.3](#). For subjects meeting exclusionary results on the C-SSRS, SBQ-R and PHQ-8, it is recommended the subject's primary care physician (PCP) should be informed, and the subject referred to a mental health professional, either by the PCP or the investigator according to their usual practice.
- t. For subjects at selected study sites, photographs of treated AD will be obtained. Photographs will be utilized for illustrative purposes and not evaluated as an endpoint (see [Section 7.7.5](#)).
- u. Pruritus Numerical Rating Scale (NRS) and Night Time Itch Scale will be assessed using an eDiary, daily during the screening period and from Day 1 to 15. After Day 15, the pruritus NRS and Night Time Itch Scale will be completed only on study visit days in the eDiary. At the Screening visit, site staff will dispense the ePRO device and review instructions for completion of the subject eDiary for the NRS and Night Time Itch Scale. At every visit, the study coordinator will review the eDiary for completeness and counsel the subject on how to complete the items in the daily eDiary, if needed.
- v. Pruritus and Symptoms Assessment for Atopic Dermatitis (PSAAD) will be conducted to assess the severity and frequency of pruritus, symptoms and sleep collected daily in a subject e-diary during the screening period and from Day 1 through the End of Study visit in selected countries (See [Section 7.8.8](#)). At the Screening visit, site staff will dispense the ePRO device and review instructions for completion of the subject eDiary for the PSAAD questionnaire. Subjects will be asked to record their assessment in their eDiary once a day before taking the investigational product. At every visit, the study coordinator will review the eDiary for completeness and counsel the subject on how to complete the items in the daily eDiary, if needed.
- w. DLQI will be completed by adult subjects only. Adolescents 12-17 years of age will complete the CDLQI instead.
- x. SF-36v2 and WPAI:AD will be completed by adult subjects only. Adolescents 12-17 years of age will not complete these assessments.

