9.2.4. Analysis of Secondary Endpoints

The key secondary endpoints which are expressed as proportions such as EASI50, EASI90 and the proportion of subjects achieving a 4-point improvement from baseline in the pruritus NRS measure will be analyzed using the same method as the for co-primary endpoints. This

would also apply to any other binary endpoint in the study. Endpoints which are continuous will be analyzed as described below.

For continuous endpoints, such as percent change from baseline in the EASI total score, a mixed-effect model with repeated measures (MMRM) will be used. This model will include the factors (fixed effects) for treatment group, randomization strata (age group, disease severity), visit, treatment-by-visit interaction, and relevant baseline value. Within the framework of MMRM, the treatment difference will be tested at the pre-specified primary time point, Week 12, as well as at the other time points by time point-specific contrasts from the MMRM model.

Continuous endpoints such as the change from baseline in **CCI**

[REDACTED] For binary endpoints such as the SCORAD50 or SCORAD75 or the proportion of subjects with PtGA of AD of clear (0) or almost clear (1) and ≥ 2 point improvement from baseline over 12 weeks, the same method as used for the binary endpoints in [Section 9.2.3](#) will be employed. All secondary endpoints except the key secondary endpoints will be evaluated at the 5% level of significance, without adjustments for multiple comparisons.

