3.4. Baseline Variables

In general, for all analyses, baseline will be defined based on observations collected prior to first dose. Baseline values for demographics, medical and other history, atopic dermatitis history will be based on measures collected at Visit 1 / Screening visit. Study Day 1 is defined as the day the subject receives first dose of study drug. For purposes of all other analyses including analyses for change from baseline, the baseline value will be defined as measured on Day 1 (before time of first dose, if time is available). If a value is missing on Day 1, then the last available observation before Day 1 will be used. For the PSAAD score, baseline will be defined as the average of all values recorded from Day -6 until Visit 2 / Day 1. For analysis purposes, randomization strata information will be taken from the Case Report Form (CRF). Baseline disease severity will be defined using the IGA score at baseline. For endpoints which are not time sensitive, measurements taken on Day 1 after the first dose may be used as baseline observations.

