5.2.3. Analyses of Longitudinal Continuous Data

Mixed-effect, repeated measures (MMRM) models will be used. The fixed effects of treatment (PF-04965842 200 mg QD and 100 mg QD and the placebo group), visit (Weeks 2, 4, 8 and 12), treatment-by-visit interaction and randomization stratification factors will be included. Visit will be modeled as a categorical covariate. Unstructured covariance matrix will be assumed for the model errors. Compound symmetry covariance matrix will be used if the model with unstructured covariance doesn't converge.

When modeling the change from baseline values, the variable for visit will start with the first post-baseline visit, and the actual baseline value will be included as a covariate. At each visit, estimates of least square mean (LSM) values and the LSM differences between the PF-04965842 treated groups and the placebo group will be derived from the model. The corresponding p-values and 95% confidence intervals will also be derived from the model.

Estimates of the difference in LSMs along with the two-sided 95% confidence interval will also be provided for the PF-04965842 200 mg QD group versus the PF-04965842 100 mg QD group. No hypotheses will be tested.

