6.3.2. Week 12 Change from Baseline in PSAAD

- Summary: Change from baseline at Week 12.
- Population: FAS, PPAS.
- Statistical Method: MMRM in [Section 5.2.3](#). As PSAAD is collected daily, data will be summarized weekly using a simple average of the values recorded within a week. In the implementation of the MMRM models, data from all weekly visits will be used
- Missing Data: Observed Data

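### The MMRM fits one baseline slope to all visits; a baseline-by-visit term would protect Week 12 PSAAD precision at almost no cost if the baseline correlation fades

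*SAP*

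**What the plan says.** SAP 5.2.3 builds the MMRM from treatment, visit and further terms: "treatment-by-visit interaction and randomization stratification factors will be included". For change from baseline it adds that "the actual baseline value will be included as a covariate". Protocol 9.2.4 ends its list of fixed effects with "visit, treatment-by-visit interaction, and relevant baseline value". Neither document crosses baseline with visit, so the two agree on a single slope.

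SAP 5.2.3 names four visits (Weeks 2, 4, 8 and 12). For PSAAD, SAP 6.3.2 replaces them: "In the implementation of the MMRM models, data from all weekly visits will be used". SAP Appendix 10 defines those values as weekly means, starting with Days 2 to 8 and running to Week 12, which makes 12 post-baseline time points. On the baseline itself, SAP 3.4 says: "For the PSAAD score, baseline will be defined as the average of all values recorded from Day -6 until Visit 2 / Day 1".

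On covariance, SAP 5.2.3 says: "Unstructured covariance matrix will be assumed for the model errors". The fallback reads: "Compound symmetry covariance matrix will be used if the model with unstructured covariance" fails to converge.

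Change in PSAAD at Week 12 is a key secondary endpoint within the multiplicity procedure (SAP 3.2.1 and 5.1). Footnote v of the protocol's Schedule of Activities limits its collection: "from Day 1 through the End of Study visit in selected countries".

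**The concern.** A diary score averaged over the week before dosing may predict the Week 1 average better than the Week 12 average. If so, the true baseline slope falls over the visits. A model with one slope estimates a weighted average of the visit slopes, and under an unstructured covariance the early, tightly correlated visits carry most of the weight. That average is then applied at Week 12, where it is too steep. Baseline variation that the right slope would have removed stays in the Week 12 treatment difference.

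At stake is some precision on an alpha-controlled endpoint that is measured in only part of the trial. The same reasoning applies, more weakly, to the four-visit MMRMs for EASI, %BSA, SCORAD and pruritus NRS.

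**Working it through.** **The plan's own figures.** The documents give no power or precision figure for PSAAD, only for the co-primary endpoints. Those reproduce by the normal approximation at two-sided 5% with 150 v 75:
- IGA, 26% v 6%: pooled rate 0.193, null SE 0.0559, alternative SE 0.0451; (0.20 − 1.96 × 0.0559)/0.0451 = 2.01, power 97.8% (stated: at least 95%).
- EASI-75, 45% v 15%: pooled rate 0.35, null SE 0.0674, alternative SE 0.0579; (0.30 − 1.96 × 0.0674)/0.0579 = 2.90, power 99.8% (stated: at least 99%).
- Joint power: 0.95 × 0.99 = 94.05% (stated: at least 94%).

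They do not bear on this point.

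**Assumed inputs for PSAAD.** SD 2 points at baseline and at every visit; correlation ρ of baseline with the weekly score falling linearly from Week 1 to Week 12; residual correlation either 0.9 per week (pattern A), or half constant and half decaying at 0.7 per week (pattern B).

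**Formula.** With equal SDs the slope of the score at visit t is ρ_t (for change it is ρ_t − 1, so differences between slopes are the same). The common slope is the generalised least squares average, b_c = (1′S⁻¹ρ)/(1′S⁻¹1), where S is the residual covariance. The ratio of Week 12 contrast variances, common slope over visit-specific slopes, is

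1 + (ρ₁₂ − b_c)² × Var(baseline) / Var(residual at Week 12) = 1 + (ρ₁₂ − b_c)² / (1 − ρ₁₂²).

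Example, 0.8 to 0.5, pattern B: b_c = 0.741, so 1 + 0.241²/0.75 = 1.077.

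| ρ, Week 1 to Week 12 | b_c (A / B) | Ratio, 12 visits (A / B) | Ratio, 4 visits (A / B) |
|---|---|---|---|
| 0.5 constant | 0.500 / 0.500 | 1.000 / 1.000 | 1.000 / 1.000 |
| 0.7 to 0.6 | 0.657 / 0.660 | 1.005 / 1.006 | 1.004 / 1.005 |
| 0.7 to 0.5 | 0.625 / 0.633 | 1.021 / 1.024 | 1.017 / 1.019 |
| 0.8 to 0.5 | 0.721 / 0.741 | 1.065 / 1.077 | 1.051 / 1.059 |
| 0.8 to 0.4 | 0.709 / 0.738 | 1.114 / 1.136 | 1.087 / 1.101 |
| 0.85 to 0.3 (extreme) | 0.780 / 0.824 | 1.253 / 1.302 | 1.183 / 1.215 |

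A separate least squares check gave 5-7% for 0.8 to 0.5 and 8-11% for 0.8 to 0.4, which sets the lower ends of the ranges in the verdict.

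**Simulation.** Both models were fitted with an estimated unstructured covariance, 12 visits and N = 375. The model-based ratios were 1.000 (constant 0.5), 1.006 (0.7 to 0.6), 1.074 (0.8 to 0.5) and 1.134 (0.8 to 0.4). The empirical ratios were 1.008, 1.007, 1.018 and 1.097, with Monte Carlo error of about 0.04. For 0.8 to 0.5 the model-based ratio was 1.083 with 12% random dropout and 1.077 at N = 250.

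**Sensitivity for 0.8 to 0.5.** About 1.03 under the compound symmetry fallback; 1.03 if the SD rises to 2.4 by Week 12; 1.12-1.13 if it falls to 1.6.

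**Meaning for power.** For an effect with 90% power under visit-specific slopes (two-sided 5%), power becomes Φ(3.242/√ratio − 1.960). Ratios of 1.02, 1.07 and 1.14 give 89.4%, 88.0% and 85.9%. As a sample-size equivalent, 375 × (1 − 1/ratio) is about 7, 25 and 46 subjects.

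**Bias.** Without baseline-dependent dropout the mean estimates of the two models agreed within 0.01 for a true effect of −2. With baseline-dependent placebo dropout of 18-22%, the common-slope estimate moved by about 0.02-0.04 SD in favour of active. A wider set of assumptions (placebo/active dropout from 15%/8% to 31%/15%, dependent on baseline in placebo only) gave 0.02-0.16 points, which is 0.01-0.08 SD or 0.07-0.5 standard errors at 150 v 75.

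**Cost of the term.** Roughly one extra degree of freedom at Week 12: 1/(375 − 6) = 0.27%, or 1/(250 − 6) = 0.41% with 250 subjects. None was visible in simulation.

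**The case against.** The strongest case against is that this is a preference. Protocol and SAP agree, the contrast is randomised and baseline-adjusted, and a single slope is a common prespecified choice. Nothing in the documents shows that the correlation fades. Week 1 is already on treatment, so its correlation with baseline may not start high. Even a 7% rise in variance widens the confidence interval by only 3-4%. All of that stands. It limits the point to an optional improvement, but it does not remove it, because the term costs next to nothing and the possible loss runs one way only.

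A reader might infer more, in four ways that the documents do not support.
- **A known loss of 14-20%.** That needs a Week 1 correlation of about 0.86-0.94 falling to 0.35-0.57, and residuals with no week-specific noise. Letting 10% or 20% of the variance be week-specific cuts the loss to 5-13% or 3-8%.
- **That the reduced PSAAD sample makes the loss worse.** The ratio is essentially the same at 250 and at 375 subjects.
- **That the estimate or the Type I error is generally compromised.** It is not. Bias needs a changing slope together with dropout that depends on baseline and differs by arm. Only the heaviest case tried (placebo dropout near 31%) moved a nominal 5% test to about 8%. The opposite claim, that bias can be ruled out, also goes too far.
- **A stated effect on the testing sequence.** The order within Sequence A is in a figure that could not be read here, so the consequence for later hypotheses cannot be traced.

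**Conclusion.** The point holds as a conditional, low-cost improvement. The model has one baseline slope for all visits, and this can lose precision at Week 12 if the baseline correlation fades over the 12 weekly averages. With equal SDs and unstructured covariance, the variance increase is 0% for a constant correlation, about 0.5-2% for 0.7 falling to 0.5-0.6, about 5-8% for 0.8 to 0.5, and about 8-14% for 0.8 to 0.4. Larger figures need a steeper fall or a Week 12 SD well below baseline. Every correlation, SD and dropout rate used is an assumption, because the documents supply none for PSAAD. Any bias is small under the dropout patterns that seem likely, and absent when dropout does not depend on baseline differently by arm. The present plan is not wrong, and its results would be interpretable as written.

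**What to change.** Before unblinding, add a baseline-by-visit interaction to the MMRM in SAP 5.2.3, so that the fixed effects are treatment, visit, treatment-by-visit, stratification factors, baseline and baseline-by-visit. For PSAAD, state that visit means the 12 weekly averages.

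The cost is 11 coefficients for PSAAD and 3 for the four-visit models, at most about 0.3-0.4% of Week 12 variance, with no extra subjects, visits or data. Protocol section 9 lets the SAP modify the planned analyses and requires a protocol amendment only for major changes to the co-primary endpoints, so a SAP amendment is enough.

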5.2.4. Analyses of Categorical Data

The frequency and percentage for each category will be presented.

5.2.5. Analyses of Time to Event Data

For a subject who experiences the event, the time to event will be the study day corresponding to the actual date of the event or the earliest visit date at which the subject has already experienced the event. For all subjects who have not experienced the event, their time to event will be right censored at the last available measurement time (or visit) used to define whether the subject experienced the associated event.

Time-to-event endpoints will be summarized using the Kaplan-Meier method and estimated survival curves will be displayed graphically. Graphs will describe the number of patients at risk over time. The median and quartiles will be estimated by the Kaplan-Meier method and 95% CI for the median and quartiles will also be provided.

The log-rank test (stratified using randomization strata) p-value will be used for comparing time to event data between each active group and the placebo group.

5.2.6. Analyses of Tier-1 and Tier-2 Events

Number and percentage of subjects with AEs over the duration of treatment will be provided for each treatment group. Tier-1 events will be analyzed using exact methods proposed by Chan and Zhang (1999). Tier-2 events will be analyzed using asymptotic methods proposed by Miettinen and Nurminen (1985). Risk differences (each PF-04965842 dose compared to placebo) and 2-sided 95% confidence intervals will be reported. P-values will also be reported for Tier-1 events. Tier-3 events will not be summarized separately but included within the summary of all AEs.

5.3. Methods to Manage Missing Data

In general, for analyses using descriptive statistics, missing values will not be imputed. In addition, for safety endpoints, missing values will not be imputed. Other methods for handling missing values are discussed below.

5.3.1. Binary Endpoints

For binary endpoints analyzed at each scheduled visit separately, visit windows (see [Appendix 2](#)) will be used to map all observed data into nominal visits. After mapping, for subjects who drop out for any reason, any missing data will be defined as “non-responsive” from that point on at all subsequent visits; for other subjects, any observations missing intermittently (including baseline values) will be considered missing completely at random (MCAR) and will remain missing in the analysis.

Additional analyses that are based on statistical considerations will utilize the longitudinal nature of the binary endpoint. A Generalized Linear Mixed Model (GLMM) will be fit to the observed data (i.e., without defining missing data due to dropout as “non-response”). The binary outcome will be modeled using a logistic-normal distribution. Fixed factors will include treatment (PF-04965842 200 mg QD and 100 mg QD and the placebo group), visit (Weeks 2, 4, 8 and 12) and treatment-by-visit interaction. Visit will be modeled as a categorical covariate. A subject-specific random intercept will be used to model the correlation within a subject over time (see [Appendix 3](#)). Missing observations for the active groups will be imputed multiply using a tipping point analysis to estimate the treatment effect under the assumption that the missing data mechanism is missing at random (MAR) or more generally, is missing not at random (MNAR). Using the estimated posterior predictive distribution of the GLMM model parameters obtained using Markov Chain Monte Carlo (MCMC) methods, estimates of the posterior predictive probability of response will be calculated for each treatment group. For subjects with missing data at a visit, the posterior predictive response probability in each PF-04965842 dose group will be re-defined as a weighted linear combination of the posterior predictive response probability from this group and the posterior predictive response probability from the placebo group, where the missing observations in placebo group are assumed to be missing at random (MAR) (see [Appendix 3](#)). These weights are fixed MNAR quantities for the active groups. A single imputation of the missing value will be sampled from a Bernoulli distribution with this

corresponding shifted / re-defined probability of response for the PF-04965842 dose groups. This imputation will be repeated multiple times with different MCMC samples to obtain multiple completed datasets. For each such completed dataset, the estimates of the proportions and CMH-weighted difference of proportions between each PF-04965842 dose group and placebo will be obtained along with the associated standard errors using the methods in [Section 5.2.1](#). Rubin's rule (Rubin, 1987) will be used to combine the multiple estimates and standard errors across the imputed datasets and provide p-values.

The above analysis can be repeated for different combinations of MNAR quantities which will be applied to the probability of response to assess when the conclusion might change (ie, tipping). Two important scenarios are included in the tipping point analysis framework. When the MNAR quantities are zero and the posterior predictive probabilities in the PF-04965842 dose groups are not shifted, results are obtained under an assumption of MAR for the missing data mechanism. Alternatively, at the other extreme, when the MNAR quantities are 1.0 for each PF-04965842 dose group, results are obtained under an assumption that the distribution of the missing responses after discontinuation of either dose of PF-04965842 is the same as that of the missing responses on the placebo arm. More detailed descriptions are provided in [Appendix 3](#).

Due to a technical error in the process of transmission and collection of electronic data with the device, the data on the pruritus NRS scale was not collected from several subjects at the scheduled visits of Week 2 (Day 15) and after. This was not restricted to a particular site or country and was not indicative of being related to the missing value of pruritus endpoint or any other endpoints. As such, the missing data mechanism may be reasonably assumed to be missing completely at random or missing at random.

For the binary endpoints derived from the pruritus NRS, a hybrid approach will be used which is partially based on the multiple imputation method described in the previous paragraph. For this analysis, all data missing due to dropouts will be defined as "non-responsive" as described in the first paragraph, but any other data which remains missing at any intermittent visits will be handled using multiple imputation under the MAR assumption (which may be obtained by substituting the MNAR quantities as zero in the analysis described in the previous paragraph; see also, [Appendix 3](#)). At any particular visit, if there are 5 or fewer subjects with missing data in each treatment group after applying the non-responder definition, no imputations will be performed, and the data will remain missing. Note that, as described in the previous paragraphs, the GLMM will be fit to the observed data (ie, without defining missing data due to dropout as "non-response").

